10.3.2.1 Assessment of Clinical Laboratory Variables

Analyses of hematology, chemistry, and urinalysis variables which are measured longitudinally will be performed by visits and by treatment groups. For analysis at each

visit, the following summary statistics of visit values will be presented for each treatment group: sample size, mean, standard deviation, minimum, median, and maximum.

An ANOVA model with treatment as a factor will be used to compare change from baseline between different treatment groups for selected laboratory parameters. Mean difference from placebo/ADA and associated 95% CIs will be presented. The analysis applies to the following laboratory parameters of clinical interest: hemoglobin, platelets, lymphocytes, neutrophils, creatinine, ALT, AST, creatine phosphokinase (CPK), LDL, HDL, total cholesterol/HDL-cholesterol, LDL-cholesterol/HDL-cholesterol, and total cholesterol.

[figure not shown]

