8.1.5.3 Analysis of Laboratory and Vital Sign Data

Summary statistics by visit, and changes from baseline to minimum value, maximum value, and final values in continuous laboratory data, and vital signs will be summarized by treatment group.

Baseline values are defined as the last non-missing measurements recorded on or before the date of the first dose of study drug in Period 1.

The laboratory data will be categorized as Grade 0, Grade 1, Grade 2, Grade 3, and Grade 4 based on National Cancer Institute (NCI) Common Toxicity Criteria for Adverse Events (CTCAE). The shift tables will tabulate the number and percentage of subjects with baseline and post-baseline values by the above categories.

[figure not shown]
Descriptive summary and listings will be provided for potentially clinically significant laboratory values and vital signs.

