Appendix C. Study Activities

[figure not shown]
Activity	SCR D -35 to D -1	BL D	Wk 2 D 15	Wk 4 D 29	Wk 8 D 57	Wk 12 D 85	Wk 16 D 113	Wk 20 D 141	Wk 24 D 169	Wk 28 D 197	Wk 32 D 225	Wk 36 D 253	Wk 44 D 309	Wk 56 D 393	Wk 68 ^a to Wk 248 (Every 12 Wks) D 477 to D 1737	Wk 260 or PD D 1821	30 Day F/U Visit/ Call ^b D 1851	70- Day F/U Call ^b D 1877
Informed Consent ^c	X																	
Inclusion/Exclusion Criteria	X	X																
CASPAR Criteria	X																	
Medical/Surgical History ^d	X	X																
Vital Signs ^e /Weight/Height ^f	X	X	X	X	X	X	X	X	X	X	X	X	X	X	X	X	X	
Alcohol/Nicotine Use	X																	
Prior/Concomitant Therapy ^g	X	X	X	X	X	X	X	X	X	X	X	X ^g	X	X	X	X	X	
Physical Exam ^h	X	X							X					X	X^h	X		
12-Lead ECG	X ⁱ													X	X ⁱ			
															Yearly, only if required by local regulations			
Chest X-Ray ^{k,1}	X^k													X^{l}	X^{l}	X ^l		
Bilateral X-Rays of Hands and Feet ^{m,n}	X ^{m, n}						X ^m		X ^m					X ^m	X ^m	X ^m		
Serum Pregnancy Test at Central Lab ^o	X																	
Local Urine Pregnancy Test ^{p,q}		X	X	X	X	X	X	X	X	X	X	X^q	X^q	X^q	X^q	X	X	
Latent TB Risk Factor Questionnaire ^r	X													X	X^{r}	X		

ABT-494 M15-572 Protocol Amendment 8 EudraCT 2016-004130-24

Activity	SCR D -35 to D -1	BL D 1	Wk 2 D 15	Wk 4 D 29	Wk 8 D 57	Wk 12 D 85	Wk 16 D 113	Wk 20 D 141	Wk 24 D 169	Wk 28 D 197	Wk 32 D 225	Wk 36 D 253	Wk 44 D 309	Wk 56 D 393	Wk 68 ^a to Wk 248 (Every 12 Wks) D 477 to D 1737	Wk 260 or PD D 1821	30 Day F/U Visit/ Call ^b D 1851	70- Day F/U Call ^b D 1877
Central Lab QuantiFeron TB Gold Test (and Local PPD Skin Test if Required) ^s	X													X	X ^s	X ^s		
Central Lab Tests ^t hs-CRP ^u Clinical Chemistry ^v Hematology (CBC) ^v Urinalysis ^w FSH ^x	X	X	X	X	X	X	X	X	X	X	X	X	X	X	X	X	X^{hh}	
Central Lab Test ^t Total Cholesterol HDL-C LDL-C Triglycerides		X		X		X			X									
ESR (Local Lab)	X	X	X	X	X	X	X	X	X	X	X	X	X	X	X	X	X	
Other Central Lab Tests HIV Screening ^j Hepatitis B ^y and C Screening Rheumatoid Factor Anti-CCP Antibodies ANA/Reflex Anti-dsDNA	X					X ^y			X ^y			X ^y			X ^y	X ^y		
Blood Samples for upadacitinib PK Assay ^{Z,aa}			X ^z	X ^z	X ^{aa}	X ^{aa}	X ^{aa}	X ^{aa}	X ^{aa}		X ^{aa}			X ^{aa}		X ^{aa}		

ABT-494 M15-572 Protocol Amendment 8 EudraCT 2016-004130-24

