4.2 Overall Study Design and Plan

This is a Phase 3 multicenter study that includes two periods. Period 1 is 56 weeks in duration and includes a 24-week randomized, double-blind, parallel-group, placebocontrolled and active-comparator controlled period followed by an additional 32 weeks of blinded active comparator-controlled treatment (Weeks 24-56). Period 1 is designed to compare the safety, tolerability, and efficacy of upadacitinib 15 mg QD and 30 mg QD versus placebo and versus adalimumab 40 mg every other week (eow) in subjects with moderately to severely active PsA who have an inadequate response to non-biologic DMARDs (DMARD-IR). Period 1 is also designed to compare the efficacy of upadacitinib 15 mg QD and 30 mg QD versus placebo for the prevention of structural progression. Period 2 is an open-label (blinded until the last subject completes the last visit of Period 1), long-term extension of up to a total treatment duration of approximately 5 years to evaluate the safety, tolerability and efficacy of upadacitinib 15 mg QD and 30 mg QD in subjects with PsA who have completed Period 1. Starting with Amendment 6.01, subjects in Japan receiving upadacitinib 30 mg QD will be switched to upadacitinib 15 mg QD. For other countries, starting with Amendment 7 and 7.01, subjects receiving upadacitinib 30 mg QD will be switched to upadacitinib 15 mg QD.

The study is designed to enroll approximately 1640 subjects at approximately 350 study centers worldwide to meet scientific and regulatory objectives without enrolling an undue number of subjects in alignment with ethical considerations.

[figure not shown]
The study duration will include a 35-day screening period; a 56-week blinded period which includes 24 weeks of double-blind, placebo-controlled and active comparator-controlled treatment followed by 32 weeks of active comparator-controlled treatment (Period 1); a long-term extension period of up to a total treatment duration of approximately 5 years ([blinded to sites and investigators until the last subject completes the last visit of Period 1] Period 2); and a 30-day follow-up call or visit; and a 70-day follow-up call. Subjects who meet eligibility criteria will be randomized in a 2:2:2:1:1 ratio using an Interactive Response Technology (IRT) to receive double-blind study drug in one of the following treatment groups:

- Group 1: Upadacitinib 15 mg QD, N = 410 (Day 1 to Week 24) → Upadacitinib 15 mg QD (Week 24 and thereafter)

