4.3 Sample Size

The planned total sample size of approximately 1640 for this study (with 2:2:2:1:1 randomization ratio for upadacitinib 15 mg, upadacitinib 30 mg, adalimumab 40 mg eow and placebo subjects) provides at least 90% power for a 20% difference in ACR20 response rate (assuming a placebo ACR20 response rate of 30%). It will also

provide at least 90% power for the majority of the key secondary endpoints. With the given sample size, there is approximately 90% power to detect a standardized effect size of 0.26 in change from baseline in SHS for each upadacitinib dose group versus the combined placebo group at Week 24. This sample size will also provide at least 85% power for evaluating non-inferiority for each upadacitinib dose group vs. adalimumab in ACR20 response rate at Week 12 assuming 50% ACR20 response rates for adalimumab and upadacitinib and 30% ACR20 response rates for placebo. All power and sample size calculations are performed at a two-sided significance level of 0.025 and accounting for a 10% dropout rate.

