The supplementary analysis for ranked non-radiographic secondary continuous endpoints will be conducted using AO data handling and using the analysis of covariance (ANCOVA) model with treatment and the stratification factor of current DMARD use (yes/no) as the fixed factors and the corresponding baseline values as the covariates. The corresponding estimand is the difference in the mean change from baseline in the efficacy endpoints at the protocol defined time point regardless of treatment discontinuation or use of rescue medication, comparing each upadacitinib dose group vs placebo. The analysis will be conducted for those who are randomized, received study drug and have the efficacy measurement at the protocol defined time point.

For the key continuous endpoint change from baseline in HAQ-DI at Week 12, tipping point analysis will also be conducted using multiple imputation (MI) as additional supplementary analysis to explore various missing data assumptions including missing not at random (MNAR). Details of the tipping point analysis for continuous endpoints are outlined in Appendix D.

Radiographic Endpoints

For change from baseline in SHS at Week 24, statistical inference will be conducted using ANCOVA model and the associated data handling as described in Section 9.1.2 with treatment and the stratification factor of current DMARD use (yes/no) as the fixed factors and the corresponding baseline values as the covariates. The primary estimand for the x-ray assessment is the difference in the mean change from baseline in SHS score at Week 24, under the assumption that patients with missing data, including those due to

premature discontinuation of study drug or use of rescue medication, can have their measurements at Week 24 predicted using their SHS score from the baseline window and the Week 16 window. The comparison will be between each upadacitinib dose group vs placebo for patients randomized and treated with at least one dose of study drug.

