10.0 Safety Analysis

10.1 General Considerations

Safety analyses will be carried out using the Safety Analysis Set by "as treated" treatment groups. There are two sets of planned safety analysis: safety analysis by Week 24, and long-term safety analysis.

Safety Analysis through Week 24

Standard safety analysis by the "as treated" treatment groups of upadacitinib 15 mg QD, upadacitinib 30 mg QD, adalimumab 40 mg EOW and combined placebo groups will be performed on safety data up to Week 24. No protocol-defined treatment switching will occur prior to this time point.

The standard safety analyses will include reporting of adverse events (AEs), laboratory, and vital signs measurements. Frequency tables of subjects with treatment-emergent adverse events (TEAEs) by system organ class (SOC) and by preferred term (PT) as in the Medical Dictionary for Regulatory Activities (MedDRA) dictionary will be provided by as-treated treatment groups. Mean changes from baseline in all continuous laboratory parameters and vital signs variables at each visit will be summarized by "as treated" treatment groups. Frequency tables of subjects meeting criteria for potentially clinically significant vital sign values and for potentially clinically significant laboratory values will be provided by as-treated treatment groups. Missing safety data will not be imputed. Treatment comparison of upadacitinib versus placebo and ADA will be provided for key safety endpoints including overview of AE, overview of AE of special interest, change from baseline in selected laboratory parameters, and potentially clinically significant laboratory values. Treatment difference and corresponding 95% CI will be provided.

Long-Term Safety Analysis

[figure not shown]

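### Between-arm laboratory comparisons use treatment-only ANOVA on change; adding the baseline value would narrow the intervals at almost no cost

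*SAP*

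**What the plan says.** SAP 10.3.2.1, which covers laboratory data up to Week 24, states: "An ANOVA model with treatment as a factor will be used to compare change from baseline between different treatment groups for selected laboratory parameters". It continues: "Mean difference from placebo/ADA and associated 95% CIs will be presented". The 13 parameters are hemoglobin, platelets, lymphocytes, neutrophils, creatinine, ALT, AST, CPK, LDL, HDL, total cholesterol and two cholesterol ratios. Treatment is the only term named. SAP 10.1 lists change from baseline in selected laboratory parameters among the key safety endpoints compared between arms, adding: "Treatment difference and corresponding 95% CI will be provided".

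A baseline value exists for all 13. Protocol 8.1.5.3 says: "Baseline values are defined as the last non-missing measurements recorded on or before the date of the first dose of study drug". In Protocol Appendix C, chemistry and hematology are scheduled at Screening and Baseline. The row "Total Cholesterol HDL-C LDL-C Triglycerides" is marked at Baseline and Weeks 4, 12 and 24, and the ratios derive from it.

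For continuous efficacy endpoints the SAP does adjust for baseline. The MMRM in 9.1.2 has the baseline measurement as a covariate, and the ANCOVA in 9.2.3 is specified "with treatment and the stratification factor of current DMARD use (yes/no) as the fixed factors and the corresponding baseline values as the covariates". Neither document extends this to the laboratory model or explains why it is left out.

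For the long term, SAP 10.1 promises upadacitinib versus adalimumab differences with 95% CIs for selected laboratory parameters, and 10.3.3.1 promises analyses of change in hemoglobin, lymphocytes, neutrophils, creatinine and CPK. Neither names a model.

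**The concern.** A change score is usually correlated with its own baseline. When the model omits baseline, that explainable variation stays in the residual and widens the interval. It also means that, in the trial as realized, a chance difference between arms at baseline feeds into the estimated difference in change.

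Protocol 3.2 names liver tests, lipids, creatinine, CPK, hemoglobin and white cells as laboratory changes seen with upadacitinib, and describes the hemoglobin effect as depending on inflammatory burden at baseline. The Week 24 table covers largely these parameters, against both placebo and adalimumab. Readers will judge it by its intervals, so avoidable width makes a real difference harder to see and a small one harder to rule out.

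**Working it through.** **Sample size per comparison.** The documents give no figure for the laboratory analysis. The only stated power for a continuous change from baseline is about 90% for a standardized effect of 0.26 in SHS (SAP 4.3), which serves to check the n used below. Inputs: 410 per active arm and 205 + 205 = 410 on combined placebo (SAP 4.2). SAP 4.3 adds: "All power and sample size calculations are performed at a two-sided significance level of 0.025 and accounting for a 10% dropout rate". This gives 410 × 0.9 = 369 per arm.

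Power = Φ(0.26 × √(369/2) − 2.241) = Φ(3.532 − 2.241) = 0.9015, which reproduces the stated figure. In reverse, 368 per arm are needed; 368/0.9 = 409 against 410 planned. I use n = 369 per arm.

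**Variance.** Let s0 and s1 be the baseline and follow-up SDs and ρ their correlation.

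- ANOVA on change: s0² + s1² − 2ρ·s0·s1
- ANCOVA residual: s1²(1 − ρ²)
- Difference: (s0 − ρ·s1)², which is never negative

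With s0 = s1 = s these become 2s²(1 − ρ) and s²(1 − ρ²). Their ratio is (1 + ρ)/2, so the ratio of CI widths, ANCOVA to ANOVA, is √((1 + ρ)/2).

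**Baseline imbalance.** Given an observed baseline difference D, the ANOVA contrast moves by (b − 1)D, where b = ρ·s1/s0 is the slope of follow-up on baseline. With equal SDs this is −(1 − ρ)D.

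**Results** (equal SDs, n = 369 per arm, 95% half-widths in SD units; ρ is assumed):

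| ρ | ANOVA | ANCOVA | Width ratio | ANCOVA narrower by | Shift for D = 0.10 SD |
|---|---|---|---|---|---|
| 0.3 | 0.171 | 0.138 | 0.806 | 19% | −0.07 |
| 0.5 | 0.144 | 0.125 | 0.866 | 13% | −0.05 |
| 0.7 | 0.112 | 0.103 | 0.922 | 8% | −0.03 |
| 0.8 | 0.091 | 0.087 | 0.949 | 5% | −0.02 |
| 0.9 | 0.065 | 0.063 | 0.975 | 3% | −0.01 |

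**Unequal SDs.** With s1/s0 from 0.8 to 1.5 and ρ of 0.5, 0.7 and 0.9, the width ratio runs from 0.76 to 0.999. It reaches 1 only when b = 1.

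**Simulation** (2,000 trials, ρ = 0.7, n = 369 per arm, no true effect). The width ratio was 0.922. Coverage was 94.7% for ANOVA and 95.5% for ANCOVA, with mean error about 0 for both. The slope of the estimate on the observed imbalance was −0.34 for ANOVA (theory −0.30) and −0.04 for ANCOVA (theory 0).

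**The case against.** The strongest reply is that nothing here is wrong, only less efficient. A reader might infer from the missing covariate that the contrast is biased, or that regression to the mean is left uncorrected. The documents do not support that. In a randomized comparison, regression to the mean is expected equally in each arm and cancels from the difference, and the simulation shows correct coverage and no average error. Imbalance matters only conditionally on the baselines observed, and the wider ANOVA interval already allows for it. The standard error of the baseline difference is √(2/369) = 0.074 SD. An imbalance of that size at ρ = 0.7 moves the estimate by 0.3 × 0.074 = 0.022 SD, against a half-width of 0.112 SD. One qualification: safety groups are as treated, so if any subject received a treatment other than the one assigned, part of a baseline difference need not be random.

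A reader might also take these as formal contrasts. They are not. Protocol 8.1.5.1 calls the laboratory analysis descriptive, SAP 10.3.2.1 sets no hypothesis, margin or decision rule, and the multiplicity procedure in SAP 9.2.5 covers only the primary and ranked secondary endpoints. The same risks are also examined through shift tables, worsening-grade counts, liver criteria, adverse events of special interest and DMC review.

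Finally, the size rests on correlations that the documents do not give. For stable parameters it is small: at ρ = 0.95 the ANOVA interval is only 1.3% wider.

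All of this stands and limits the weight of the point. It gives no reason to leave baseline out.

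**Conclusion.** The point holds as one of precision. The Week 24 laboratory contrast is valid, but with equal SDs its intervals are wider than needed by an amount that falls as ρ rises, from 24% (ρ = 0.3) to 2.6% (ρ = 0.9) relative to ANCOVA. The direction does not depend on the assumed correlation or on equal SDs, since ANCOVA has the smaller residual variance unless the slope of follow-up on baseline is exactly 1. The size does depend on both. No power, type I error or multiplicity statement changes, and no safety conclusion is shown to be wrong.

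Two further inferences should be resisted. One is that the Week 24 model should simply be replaced. SAP 11.1 says that the primary efficacy analysis and Period 1 reporting were completed under version 3.0 and that version 4.0 applies only to later long-term reporting; Appendix F dates the Week 24 lock to January 2020. Replacement would be a post hoc change to reported, unblinded results. The other is that the long-term comparisons share the treatment-only ANOVA. The SAP names no model for them, so what exists there is a gap that can still be filled in advance.

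**What to change.** In SAP 10.1 and 10.3.3.1, name the model for the long-term upadacitinib versus adalimumab comparisons of selected laboratory parameters: ANCOVA with change from baseline as response, and treatment and the baseline value of that parameter as terms. Use the study baseline, which 10.1 already sets for mean change in laboratory values.

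For the Week 24 comparisons in 10.3.2.1, keep the reported ANOVA and add the same ANCOVA, labeled supplementary and specified after reporting.

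The cost is a sentence in each section and one covariate in the program. A subject without a baseline value already has no change score, so none is lost. Sample size, multiplicity scheme and decision rules are untouched.

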Safety results across the studies showed that upadacitinib was well tolerated and the types and frequencies of adverse events (AEs) were consistent with subjects with moderately to severely active RA receiving immunomodulatory therapy. One subject died from lung cancer 14 weeks after completing the 12-week study (Study M13-537); the lung cancer was considered by the investigator as not related to study drug. This subject had a 40 pack-year history of tobacco use and a positive family history of lung cancer. The rates of serious adverse events (SAEs) and AEs resulting in discontinuation of study drug were low and not significantly different from placebo. No trends in the number of subjects with potentially clinically significant values or changes per dose group were observed for any of the hematology or urine parameters; however, treatment-emergent increases in blood creatine phosphokinase (CPK), all of which were asymptomatic, were reported with higher doses of upadacitinib (12 to 18 mg BID). No subject discontinued study drug due to elevated CPK. In all subjects, the CPK values normalized or were significantly reduced at the time of last observation. Among subjects with laboratory evidence of systemic inflammation (as evidenced by C-reactive protein [CRP] > upper limit of normal [ULN]), treatment with upadacitinib 3 mg BID or 6 mg BID was associated with improvements in mean hemoglobin (Hgb) relative to placebo. At higher doses, there was a reduction in mean Hgb, however the reduction was not clinically significant, as mean Hgb levels remained within normal range throughout the treatment period. One subject each in the 18 mg BID group in both Study M13-550 and Study M13-537 had an AE of anemia. Overall, the AEs observed during the Phase 2 development, as well as changes in physical examination findings, vital signs and clinical laboratory results, do not indicate any safety concerns for further development of upadacitinib.

Phase 3 Studies with upadacitinib

[figure not shown]

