A bioavailability study has demonstrated that 15 mg QD and 30 mg QD regimens of the once-daily tablet formulation provide equivalent daily AUC and comparable C_{max} , and C_{min} to 6 mg BID and 12 mg BID, respectively, of the immediate-release capsule formulation used in Phase 2 studies in RA.

The mean exposures (AUC and C_{max}) for the highest dose that will be evaluated in this study (30 mg QD) are predicted to be lower than the exposures associated with the no-observed-adverse-effect level in the 9-month GLP preclinical toxicology study in dogs (1.5 mg/kg/day) and lower than the highest mean upadacitinib exposures evaluated in healthy subjects or in patients in previous clinical studies.

The adalimumab dose selected for this study, 40 mg SQ EOW, is the dose marketed for treatment of patients with PsA.

[figure not shown]

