interaction in the model. The "group" option in PROC MIXED is used to allow for heterogeneity among treatment groups in the covariance structure. The coefficient for treatment-by-time interaction is used to estimate the difference in rate of progression (per 24 weeks) comparing upadacitinib and placebo. The rate of progression (per 24 weeks) for each group respectively is also estimated using the coefficients for time and treatment-by-time interaction. In case the random coefficient model does not converge, a simplified model may be explored by removing the random intercept or fitting a fixed-effect linear effect model.

Additionally, in the event that data severely deviates from the normal distribution, non-parametric analyses such as the ranked ANCOVA may be considered for treatment comparison.

[figure not shown]

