10.3 Analysis of Laboratory Data

10.3.1 Variables and Units

All laboratory parameters to be collected in this study are listed below. Laboratory parameters will be reported using the standard international (SI) units.

[figure not shown]

Table 12. List of Laboratory Variables

Bicarbonate

Laboratory Variables	
Hematology	
White Blood Cell (WBC) Count	
Red Blood Cell (RBC) Count	
Hemoglobin	
Hematocrit	
Platelets count	
Neutrophils	
Basophils	
Eosinophils	
Lymphocytes	
Monocytes	
Bands	
Chemistry	
Total Bilirubin	
Alkaline Phosphatase (ALP)	
Aspartate aminotransferase (AST)	
Alanine aminotransferase (ALT)	
Total Protein	
Albumin	
Glucose	
Triglycerides	
Blood Urea Nitrogen (BUN)	
Creatinine	
Sodium	
Potassium	
Calcium	
Inorganic Phosphorus	
Creatine Phosphokinase (CPK)	
Chloride	

[figure not shown]

Table 12. List of Laboratory Variables (Continued)

[figure not shown]
Laboratory Variables	
Chemistry (Continued)	
Cholesterol	
LDL cholesterol	
HDL cholesterol	
LDL/HDL ratio	
Cholesterol/HDL ratio	
Urinalysis	
Specific Gravity	
рН	
Protein	
Glucose	
Ketones	
Blood	
Microscopic Examination (if needed)	
Urobilinogen	
Bilirubin	
Leukocytes	
Nitrites	
Other	
hs-CRP	
ESR	

10.3.2 Analysis of Laboratory Data by Week 24

The laboratory data will be summarized by the "as treated" treatment groups (Upadacitinib 15 mg QD, Upadacitinib 30 mg QD, ADA 40 mg EOW and combined placebo groups).

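### The laboratory ANOVA makes no allowance for unequal variances, so if spread differs by arm (plausible for CPK on 30 mg) its 95% CIs miss their nominal level; the long-term comparisons name no model

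*SAP*

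**What the plan says.** SAP 10.3.2.1 sets out the between-arm analysis of 13 laboratory parameters, among them CPK, ALT and AST: "An ANOVA model with treatment as a factor will be used to compare change from baseline between different treatment groups for selected laboratory parameters". The output follows: "Mean difference from placebo/ADA and associated 95% CIs will be presented". SAP 10.3.2 lists the groups: "Upadacitinib 15 mg QD, Upadacitinib 30 mg QD, ADA 40 mg EOW and combined placebo groups". The section states no transformation, covariate, robust standard error or unequal-variance option. It does not say whether one four-arm model or separate two-arm models are fitted, and it gives no code.

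SAP 10.1 also plans upadacitinib versus adalimumab differences with 95% CIs for selected laboratory parameters in the long-term analysis. SAP 10.3.3.1 lists hemoglobin, lymphocytes, neutrophils, creatinine and CPK for long-term change from baseline. Neither section names a model.

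Elsewhere the SAP does allow for unequal spread. In the random coefficient sensitivity analysis of SHS (SAP 9.2.3), the group option "is used to allow for heterogeneity among treatment groups in the covariance structure". The tipping-point ANCOVA in Appendix D uses sandwich errors.

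**The concern.** An ordinary ANOVA with treatment as the factor estimates one error variance from all arms and uses it for every contrast. That is harmless when the arms share a variance. The protocol gives a reason to doubt this for CPK. In Phase 2 rheumatoid arthritis (Protocol 3.0), CPK increases, "all of which were asymptomatic, were reported with higher doses of upadacitinib", were seen at 12 to 18 mg BID. Protocol 5.6.4 says that the 15 mg and "30 mg QD regimens of the once-daily tablet formulation provide equivalent daily AUC" to 6 mg BID and 12 mg BID respectively. The 30 mg arm therefore sits in the range where increases were reported, and the 15 mg arm sits below it. If the increases occur in only some subjects, they raise the spread as well as the mean.

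The pooled model would then lend the smaller variances of the other arms to the 30 mg contrast, and the larger 30 mg variance to the 15 mg contrast. CPK elevation is an adverse event of special interest (Protocol 6.1.1.3), so an interval that understates uncertainty for the higher dose and overstates it for the lower one is unwelcome.

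**Working it through.** **Inputs from the documents.** 410 subjects each on 15 mg, 30 mg and adalimumab, and 205 + 205 = 410 on placebo (SAP 4.2). With the 10% dropout in SAP 4.3, n = 410 × 0.9 = 369 per arm. The nominal level is 95% (SAP 10.3.2.1).

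**Assumed.** The SDs of change by arm, because the documents give none. They are shown as ratios in the order 15 mg : 30 mg : adalimumab : placebo.

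**Formulas (equal n).** For arms i and j:
- pooled four-arm SE² = 2 × mean(s²) / n
- true SE² = (s_i² + s_j²) / n
- width ratio r = √[2 × mean(s²) / (s_i² + s_j²)]
- coverage ≈ 2Φ(1.96 r) − 1

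n cancels from r, so dropout that is equal across arms does not matter.

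**The plan's figure first.** At 1:1:1:1, r = √(2/2) = 1 and coverage is 95.0%. The nominal level reproduces.

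**30 mg versus placebo, worked for 1:2:1:1.** Mean variance = (1 + 4 + 1 + 1)/4 = 1.75.
- 30 mg: r = √(3.5/5) = 0.837, and 2Φ(1.640) − 1 = 89.9%.
- 15 mg: r = √(3.5/2) = 1.323, and 2Φ(2.593) − 1 = 99.0%.

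| SD ratios | r, 30 mg | r, 15 mg | Coverage, 30 mg / 15 mg vs placebo |
|---|---|---|---|
| 1:1.25:1:1 | 0.944 | 1.068 | 93.6 / 96.4% |
| 1:1.5:1:1 | 0.899 | 1.146 | 92.2 / 97.5% |
| 1:2:1:1 | 0.837 | 1.323 | 89.9 / 99.0% |
| 1.5:2:1:1 | 0.908 | 1.127 | 92.5 / 97.3% |
| 1.5:1.5:1:1 | 1.000 | 1.000 | 95.0 / 95.0% |
| 1.5:1:1:1 | 1.146 | 0.899 | 97.5 / 92.2% |
| 1:1:1:1.5 | 0.899 | 0.899 | 92.2 / 92.2% |
| 1:1:1.5:1 | 1.146 | 1.146 | 97.5 / 97.5% |

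In general, the 30 mg versus placebo interval is too narrow only if s₃₀² + s_P² exceeds s₁₅² + s_A². The 15 mg versus placebo interval is too wide only if s₁₅² + s_P² is less than s₃₀² + s_A².

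**Is skew the cause?** A simulation on the reported scale (20,000 runs, 369 per arm, log-normal data with log-SD 0.5 and 1.0) says not. With equal SDs, the four-arm pooled intervals covered 94.9% to 95.3%. At 1:2:1:1 they covered 90.1% to 90.6% (30 mg) and 98.9% to 99.0% (15 mg). Arm-specific variances, without any log transformation, gave 94.5% to 95.4% throughout.

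**Two-arm fits.** With equal n, two-arm pooling gives SE² = [(s_i² + s_j²)/2] × (2/n) = (s_i² + s_j²)/n, which is already correct. With unequal n it is not. Take, as an assumed illustration, 205 left on 30 mg against 410 on adalimumab, with an SD ratio of 1.5:
- pooled variance = (204 × 2.25 + 409 × 1)/613 = 1.416
- pooled SE² = 1.416 × (1/205 + 1/410) = 0.01036
- true SE² = 2.25/205 + 1/410 = 0.01341
- r = √(0.01036/0.01341) = 0.879, coverage 91.5%

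At an SD ratio of 2 the same steps give r = 0.816 and coverage 89.0%.

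**The case against.** The SAP never says raw scale, four-arm fit or pooled variance; those are defaults read into a silent text. The sample code in Appendix A, for a different test, subsets to two arms, and with equal n two-arm fits remove the problem. This stands as a limit on the claim for Week 24, but it does not carry over to unequal group sizes.

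A reader might infer that the 30 mg intervals are in fact too narrow and the 15 mg intervals too wide. The documents do not support that as a statement of fact: they report no spread by arm, and other SD patterns remove or reverse the effect. Nor do they support extending the direction to ALT and AST, where Protocol 3.2 mentions liver test elevations without a dose relation.

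A reader might also blame the reported scale and ask for logs. Skew alone leaves coverage near 95% at this sample size, and a log ratio changes what is estimated.

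These intervals are not the only evidence either. Special-interest event summaries, grade shifts, potentially clinically significant values and liver-threshold counts (SAP 10.2.1.6 and 10.3.2.2 to 10.3.2.4) do not use this model. No test or decision rule hangs on the intervals, and no 30 mg versus 15 mg contrast is planned here.

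The SAP's unequal-variance provisions sit in sensitivity and supplementary analyses; its primary ANCOVA and MMRM specify none. That weakens the charge of inconsistency.

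Finally, SAP 11.1 says primary and Period 1 reporting is complete and version 4.0 governs only future long-term reporting. That is correct, and it moves the useful change to the long-term comparisons.

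**Conclusion.** The point holds conditionally. If the plain ANOVA is fitted as one four-arm model and spread differs by arm, its intervals miss 95%. If spread is largest on 30 mg, coverage falls by about 1.4 points for 30 mg versus placebo at an SD ratio of 1.25 and by about 5 points at a ratio of 2, while the 15 mg interval becomes too wide. The SD ratios are assumptions. Only for CPK do the documents give a reason, and a qualitative one, to expect that ordering.

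The matter is still live for the long-term upadacitinib versus adalimumab comparisons. SAP 10.1 and 10.3.3.1 censor by-visit 30 mg laboratory data at the switch to 15 mg, and SAP 7.0 notes that the switch visit can differ between subjects. The 30 mg numbers will therefore fall relative to adalimumab, and two-arm pooling would not cure unequal variances.

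**What to change.** In SAP 10.3.2.1, state that the mean difference on the reported scale is kept and that residual variances are arm-specific, for example PROC MIXED with REPEATED / GROUP=treatment and Satterthwaite degrees of freedom, or unequal-variance contrasts. Name the same model for the long-term upadacitinib versus adalimumab laboratory comparisons in SAP 10.1 and 10.3.3.1. For the completed Week 24 analysis, run it once as a supportive check. A log-ratio analysis of CPK may be added for interpretation but is not needed for coverage.

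The cost is a few lines of text and code. If the arms truly share one variance, the price is slightly less precise variance estimates: with 369 per arm the degrees of freedom drop from 4 × 369 − 4 = 1,472 to about 2 × 369 − 2 = 736. That moves the critical value from 1.962 to 1.963.
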